### 3.2 Safety Assessments

The Primary Objective of this study is to assess patient safety across increasing infusion dose levels of Thrombosomes. This will be principally achieved by monitoring patterns in the incidence of AEs and, in particular, SAEs. An AE is any untoward or unfavorable medical occurrence in a study subject that does not necessarily have an underlying relationship with the investigational product. An AE can be any undesirable sign (e.g., an abnormal physical exam or laboratory finding), symptom, or disease, temporally associated with use of the investigational product. As described in Section 2.2.1, Primary Endpoints, safety assessments supporting the identification of AEs will include:

- Coagulation measures.
- Hematology measures.
- Routine serum chemistry measures.
- Special serum chemistry measures (troponin).
- Vital signs, plus pulse oximetry readings.
- 12-lead EKG measures.
- Physical/neurologic status.

All AEs will be described by (a) timing of the event relative to infusion start (pre-treatment AE vs. treatment-emergent AE [TEAE]), (b) system organ class (SOC) and preferred term (PT) per version 20.0 of the Medical Dictionary for Regulatory Activities (MedDRA), (c) seriousness of the event (i.e., classification as SAE), (d) criteria satisfied for SAE classification, (e) severity of the event, (f) relationship with the underlying disease, and (g) relationship with the investigational product. While data will be reported for all AEs documented within the study (i.e., both non-serious and serious), data describing all AEs will be analyzed through the Day-6 visit, and data specifically describing SAEs will be analyzed through the Day-30 visit.

An SAE is an AE that may be significant enough to lead to changes in the way the investigational product is developed or administered (e.g., adjustment to dose levels, target population, monitoring schemes, and patient consent forms). Furthermore, an SAE may result in any of the following outcomes, which, in this study, represent criteria for AE categorization as “serious”.

- Death
- Life-threatening situation (patient is at immediate risk of death)
- In-patient hospitalization (excluding those for study therapy or placement of an indwelling catheter, unless associated with other SAEs)
- Prolongation of existing hospitalization
- Persistent or significant incapacity or substantial disruption of the ability to conduct normal life functions
- Congenital anomaly/birth defect in the offspring of a patient who received study drug
- Other important medical events that may not be immediately life-threatening or result in death or hospitalization but, based upon appropriate medical and scientific judgment, may jeopardize the patient or require medical or surgical intervention to prevent the outcomes listed above

Event severity will be graded on a scale of 1-5 per version 4.0 of the National Cancer Institute Common Terminology Criteria for Adverse Events (NCI-CTCAE), with grades defined as shown below. All events of grade 4 or 5 will be reported as SAEs.

- Grade 1 (mild): Does not interfere with routine activities; minimal level of discomfort
- Grade 2 (moderate): Interferes with routine activities; moderate level of discomfort
- Grade 3 (severe): Unable to perform routine activities; significant level of discomfort
- Grade 4 (life-threatening): Requires hospitalization or emergency room visit
- Grade 5 (fatal): Results in death

In this study, an AE will be considered potentially attributable (related) to the investigational product if a high degree of certainty exists that (1) Thrombosomes presents a plausible biologic mechanism of action for causing the AE, (2) a temporal association exists between timing of the Thrombosomes infusion and onset of the AE, and (3) the AE itself cannot be explained by known

---

characteristics or conditions of the patient (e.g., underlying disease, concurrent illness) or other factors (e.g., use of concomitant medications). Categories of relatedness will include:

- Not related: No relationship to investigational product; applies to events for which evidence exists of an alternate etiology.
- Unlikely: Likely unrelated to the investigational product; likely related to factors other than the investigational product but relationship cannot be ruled out with certainty.
- Possibly: A temporal association between the AE and the administration of investigational product cannot be ruled out, but there may also be alternative etiologies such as the patient's clinical status or use of other therapies.
- Probably: A high degree of certainty of the relationship between the event and investigational product exists; a reasonable temporal association is recognized and the event cannot be explained by known patient characteristics or other factors.
- Definite: An association exists between receipt of the investigational product and occurrence of the event; any association with other factors has been ruled out.

***Suspension Rule:*** This study will be suspended if an SAE is reported by a Principal Investigator (PI) who believes that the event is possibly, probably, or definitely related to the use of Thrombosomes but does not meet the study's stopping criteria (described below). Following SAE reporting by the PI, the Sponsor will corroborate relatedness of the SAE to the study product and suspend the enrollment and infusion of patients until further evaluation of the SAE is completed. A DMC, along with the Medical Monitor and PI who treated the patient, will meet ad hoc to review characteristics and outcomes of the event. The DMC will formulate final conclusions regarding SAE causality and provide recommendations for whether the study should proceed without changes, proceed with changes, or not proceed at all.

***Stopping Rule:*** The Sponsor will stop patient enrollment if a reported SAE satisfies all 3 of the following criteria: (1) reported as death, a thrombotic or embolic event, an acute lung injury, or anaphylaxis; (2) reported within 48 hours of infusion with Thrombosomes (except for anaphylaxis, requiring reporting within 4 hours of infusion); and (3) considered to be probably or definitely directly related to Thrombosomes. If the study is stopped, the study will resume only after a complete review of the data has been performed by the Medical Monitor, all PIs, and the DMC and a determination has been made of reasonable doubt that the event is related to the product. Note that thrombotic and embolic events, collectively, include myocardial infarction, pulmonary embolism, venous thromboembolism, stroke, and transient ischemic attack. The CSP Appendices C, D, E, and G provide definitions for these events, as well as acute lung injury and anaphylaxis.

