### **1.9.8 Stopping Rules and Procedures for Study**

#### **Suspension Rules**

If an SAE is reported to the Sponsor that:

1. the investigator believes is possibly, probably, or definitely related to the use of the product (As defined in 1.22.6.1 Definition of Terms), and
2. does not meet the stopping rules criteria for SAEs listed below, then the Sponsor will confirm relatedness and suspend enrollment and infusion of patients in the study until further evaluation of the SAE is completed. The independent DMC will meet ad hoc to review the results of the event(s) with the Medical Monitor and PI who treated the patient. The DMC will then determine causality and recommend whether the study should either proceed without changes, proceed with modifications, or not proceed. See 1.22.6.4 Adverse Event Reporting for reporting of serious adverse events. Safety reports will be provided to FDA in accordance with 21 CFR 312.32.

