#### **Stopping Rules**

The Sponsor will stop enrollment into the study if an SAE of death, thrombotic or embolic event, acute lung injury or anaphylaxis occurs that is directly (probably or definite) related to the product within 48 hours of infusion of Thrombosomes (except for anaphylaxis within 4 hours). If the study is stopped, the study will be restarted only after a complete review of the data is completed by the medical monitor, all PIs and the independent DMC, and it is determined that there is reasonable doubt that the event is related to the product. Safety reports will be provided to FDA in accordance with 21 CFR 312.32.

The following definitions will be used to characterize specific stopping rule SAEs:

- Thrombotic or embolic event (including myocardial infarction, pulmonary embolism, and venous thromboembolism [defined in Appendix C- Definition of Myocardial Infarction and Appendix E- DVT and PE Algorithm Pages from ICSI Guideline, respectively], or stroke [including transient ischemic attack]). A minor catheter thrombosis is not included in this category, or
- Pulmonary adverse event of acute lung injury (ALI) (defined in Appendix D- Definition of ALI), or
- Anaphylaxis (defined in Appendix G – Modified Definition of Anaphylaxis)

An SAE will be considered potentially attributable to the product if there is a high degree of certainty that 1) a relationship to a Thrombosomes infusion exists, 2) there is a reasonable temporal association, and 3) the event cannot be explained by known characteristics of the patient's clinical state or factors including other therapy. For an SAE to be considered to be definitely related to a Thrombosomes infusion, an association exists between the receipt of an investigational product and the event, and an association to other factors has been ruled out (See 1.22.6.2 Relationship to Investigational Product for definitions to determine causality).

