#### **1.22.6.4 Adverse Event Reporting**

The PI is responsible for reporting all adverse events or unanticipated events to the local IRB, as required, and to Cellphire on a schedule related to the seriousness of the event. A case report form will be provided for these reports. Events that meet the definition of "serious," including unexpected adverse reactions (SUSARs), thrombotic adverse events, and deaths as described above, must be entered into the electronic data capture (EDC).

All SAEs must be reported to Cellphire and or Sponsor's designee, the Contract Research Organization (CRO), in the EDC within 24 hours of the Investigator becoming aware of the SAE. If the site is unable to enter the event information into EDC for any reason the site can alternatively complete the paper SAE Form, which should be faxed/mailed within 24 hours from the point in time when the investigator becomes aware of the SAE. In addition, all SAEs that occur up to and including 30 days after administration of Thrombosomes must be reported to

the Sponsor or Sponsor's designee within 24 hours from when the investigator becomes aware of the SAE.

To report an SAE, sites will enter the SAE information into the EDC or complete an SAE Report and send the SAE report to the CRO, Clinipace Worldwide, Inc.

The investigator must report new significant follow-up information for these events to the Sponsor's designee immediately (i.e., no more than 24 hours after becoming aware of the information).

Cellphire is responsible for reporting to the DMC and the FDA according to the charter, policies and applicable guidance or regulations.

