**Anaphylaxis is defined when any 1 of the 3 criteria are fulfilled:**

1. Acute onset of an illness (up to 4 hours post-infusion) with involvement of Skin/mucosal tissue (eg, hives, generalized itch/flush, swollen lips/tongue/uvula), and Airway compromise (eg, dyspnea, wheeze/bronchospasm, stridor, reduced PEF), or Reduced Blood Pressure\* or associated symptoms (eg, syncope)
2. Two or more of the following after exposure to known allergen for that patient (up to 4 hours post-infusion)  
History of severe allergic reaction  
Skin/mucosal tissue (eg, hives, generalized itch/flush, swollen lips/tongue/uvula)  
Airway compromise (eg, dyspnea, wheeze/bronchospasm, stridor, reduced PEF)  
Reduced BP\* or associated symptoms (eg, syncope)
3. Hypotension\* after exposure to known allergen for that patient (up to 4 hours post-infusion)  
\*Systolic BP <100 mm Hg or >30% drop from their baseline

BP: Blood pressure PEF: peak expiratory flow.

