determination of eligibility. Given determination of eligibility through either scenario (i.e., completion of updated screening or rescreening assessments), the patient will be immediately scheduled for infusion with Thrombosomes to occur within 4 days. Patients who are not infused within 4 days of eligibility determination will (re-)enter rescreening, if no more than 4 weeks have passed since initiation of screening. Patients who are not infused within 4 weeks of initiation of screening will no longer be actively monitored for study eligibility or scheduled for infusion. However, they may subsequently re-enter the screening process at any time, if actively bleeding or determined to be at risk of bleeding. Patients will be classified as enrolled in the study at the onset of infusion.

Activities and assessments relating to the pre-infusion (screening) period, infusion (Day 1), and the post-infusion period (follow-up through Day 30 +2 days) will be performed as indicated in **Table 2** (see Section 3.3, Summary of Activities and Assessments). Importantly, stipulations exist concerning patient enrollment and the performance of assessments. For instance, patient infusions cannot occur on the same day. Once an eligible patient has been infused, the patient must reach Day 4 without a suspension or stopping rule event being reported before a subsequent patient may be infused (see Section 3.2, Safety Assessments). In addition, a 2-week interval of non-enrollment (i.e., no infusions), with all patients on study having completed the planned Day-6 follow-up visit (on Day 6 +4 days), must be met between cohorts to allow for an independent Data Monitoring Committee (DMC) to review all safety data from the previous cohort and provide recommendations on whether the study should advance to the next cohort (see **Appendix 1**).

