## 13 APPENDICES

### 13.1 Appendix 1 – Data Monitoring Committee

An independent Data Monitoring Committee (DMC) is required for this study and will function as the primary data and safety advisory group (see also the Cellphire 2017-1 DMC Charter for more information). The DMC will periodically review study results, evaluate the treatments for adverse events and serious adverse events, and make recommendations to Cellphire, which has the responsibility to accept, reject, or to modify the DMC's recommendations. The primary purpose of the DMC is to oversee the safety of the trials and make recommendations regarding the continuation, modification or termination of the study based on the adverse effects of Thrombosomes.

The DMC will monitor study progress and any patient deaths, SAEs, severe AEs, study withdrawals, and adherence to/use of suspension rules and stopping rules. Information regarding other safety variables (e.g., AEs from laboratory results) will be also be reviewed. Specifically, study progress and safety data that will routinely be reviewed in the DMC meetings include:

- All SAEs, AEs, and use of suspension and stopping rule criteria (see Section 3.2)
- Number of patients screened
- Number of patients who resulted in a screen failure and reasons for failed entry into the study
- Number of patients enrolled
- Number of patients who withdrew from the study and reasons for withdrawal
- Number of patients evaluable (i.e., those participating through Day 6)
- Number of patients who completed study.

The DMC will make recommendations to Cellphire concerning the continuation of the study based on their periodic or ad hoc review of the data at the end of each meeting. All records of DMC recommendations made at the end of each meeting will be provided to Clinipace by Cellphire. The DMC may provide the following recommendations to Cellphire:

- Continue the study according to the protocol and any related amendments.
- Modify the study protocol. Modifications could include, but are not limited to, inclusion/exclusion criteria, frequency of visits or safety monitoring, alterations in study procedure(s), or changes in duration of observation and follow-up.
- Discontinue the study (with provisions for orderly discontinuation in accord with good medical practice).
- Other recommendations (e.g., inform the investigators and patients of a safety concern).

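### SAP 3.2 times the stopping rule by when an SAE is reported; the protocol times it by when the event occurs, so an event reported on time can meet the protocol's rule and miss the SAP's.

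*SAP*

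**What the plan says.** Both documents stop enrollment for an SAE of death, thrombotic or embolic event, acute lung injury or anaphylaxis that is probably or definitely related to the product. They differ on the clock.

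- **Protocol 1.9.8, Stopping Rules:** enrollment stops if one of the listed events, the last being "anaphylaxis occurs that is directly (probably or definite) related to the product within 48 hours of infusion of Thrombosomes", with 4 hours in place of 48 for anaphylaxis. The verb is *occurs*.
- **Protocol Appendix G:** the first anaphylaxis criterion is "Acute onset of an illness (up to 4 hours post-infusion) with involvement of Skin/mucosal tissue" plus airway or blood pressure involvement. The 4 hours run to onset.
- **SAP 3.2, Stopping Rule:** three criteria must all hold, and the second is that the SAE be "reported within 48 hours of infusion with Thrombosomes (except for anaphylaxis, requiring reporting within 4 hours of infusion". The verb is *reported*.
- **Protocol 1.22.6.4:** an SAE must be entered "in the EDC within 24 hours of the Investigator becoming aware of the SAE".

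Two other parts of the SAP rely on Section 3.2. The Day-4 gate in SAP 3.1 requires the last patient infused to reach Day 4 "without a suspension or stopping rule event being reported before a subsequent patient may be infused (see Section 3.2, Safety Assessments"). SAP Appendix 1 lists among the items the DMC routinely reviews: "All SAEs, AEs, and use of suspension and stopping rule criteria (see Section 3.2"). SAP 2.1.1 also names application of the suspension or stopping rules as an indicator of safety for the primary objective.

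**The concern.** An event cannot be reported before it happens. Every event that meets the SAP clock therefore meets the protocol clock, but the reverse is not true. A site that follows the protocol's reporting rule exactly can produce an event that stops the study under the protocol and does not stop it under the SAP.

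The SAP is also at odds with its own source. It sends the reader to protocol Appendix G for the definition of anaphylaxis, which runs on onset, and then adds a reporting deadline that Appendix G does not contain.

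The stake is the restart condition. After a stop, the study resumes only once the medical monitor, all PIs and the DMC have reviewed the data and "a determination has been made of reasonable doubt that the event is related to the product". After a suspension, the DMC reviews the event with the medical monitor and the treating PI, and may recommend going on unchanged. The difference matters for a probably related embolism or anaphylaxis in a trial whose target dose doubles at each step.

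**Working it through.** There is no sample-size, power or alpha figure to reproduce here. The check is on timing.

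**Inputs**

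- Window W: 48 h, or 4 h for anaphylaxis (protocol 1.9.8; SAP 3.2).
- Reporting allowance: up to 24 h after awareness (protocol 1.22.6.4).
- Assumption: awareness coincides with onset. Later awareness widens the gap.

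**Rules.** Let t be hours from infusion to onset and d the hours from onset to report.

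- Protocol rule met on timing: t ≤ W.
- SAP rule met on timing: t + d ≤ W.
- The two disagree when t ≤ W < t + d.

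**What the texts permit.** With d up to 24 h, disagreement is possible for any onset after W − 24, or after 0 if that is negative.

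| Event type | Onsets that can be reported on time and fail the SAP rule | Share of window | Latest on-time report |
|---|---|---|---|
| 48 h events | after 24 h, up to 48 h | 24/48 = 50% | 48 + 24 = 72 h |
| Anaphylaxis | 0 to 4 h | 4/4 = 100% | 4 + 24 = 28 h |

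**Examples**

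- Pulmonary embolism at 40 h, reported at 60 h (d = 20): protocol 40 ≤ 48, met; SAP 60 > 48, not met.
- Anaphylaxis at 1 h, reported at 10 h (d = 9): protocol 1 ≤ 4, met; SAP 10 > 4, not met.
- Anaphylaxis at 3.5 h: it counts under the SAP only if reported within 4 − 3.5 = 0.5 h.

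**Illustration only.** The documents give no distribution of onset or reporting lag. Take onset uniform on 0 to W and lag uniform on 0 to L. Among events that meet the protocol rule, the share that fails the SAP rule is L/(2W) when L ≤ W, and 1 − W/(2L) when L > W.

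| Maximum lag L | 48 h events | Anaphylaxis |
|---|---|---|
| 1 h | 1/96 = 1% | 1/8 = 12.5% |
| 2 h | 2/96 = 2% | 2/8 = 25% |
| 6 h | 6/96 = 6% | 1 − 4/12 = 67% |
| 24 h | 24/96 = 25% | 1 − 4/48 = 92% |

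The schedule of events has AE checks every 15 minutes to 2 h and hourly to 4 h, so the shorter lags are the more plausible ones for anaphylaxis.

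**What happens to a mismatched event.** It is still a related SAE that does not meet the stopping criteria, which is the trigger for suspension. Under the protocol's Suspension Rules the Sponsor will confirm relatedness and "suspend enrollment and infusion of patients in the study until further evaluation of the SAE is completed". The Day-4 gate responds to either kind of event, so it is unaffected. The primary endpoint counts in SAP 2.2.1, the AE summaries in SAP 8.1 and the DMC outputs in SAP Appendix 1 are not filtered by this window.

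**The case against.** The strongest reply is that the SAP does not run the trial. The Sponsor stops enrollment under protocol 1.9.8. Protocol 1.9.7 leaves the review process and stopping rules to a DMC charter, which is not among the documents. On this view SAP 3.2 is a loose paraphrase in a descriptive section, no output depends on it, and suspension protects patients almost as well. The protocol's own Day-4 gate also speaks of an event being reported, and SAP 3.2 uses the word loosely elsewhere, as in criterion (1). Finally, the percentages rest on assumed distributions for events that may never occur among 24 patients.

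Much of this stands. No analysis changes, dosing would pause either way, and a Sponsor that applies the protocol text keeps the stricter restart. The percentages should carry no weight in judging how serious this is.

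It does not remove the conflict. The criterion mentions reporting twice, the second time as a requirement within 4 hours, so reading it as onset is strained. SAP Section 11 lists the most significant departures from the protocol, and this is not among them, so nothing suggests a deliberate change. The SAP's own DMC appendix cites Section 3.2 for the stopping criteria. Someone working from it could tell the DMC that the rule was not met when under the protocol it was.

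**Conclusion.** The concern holds. The SAP's stopping rule is strictly narrower than the protocol's, and reports made within the permitted 24 hours can fall between the two. If awareness coincides with onset, that is possible for half of the 48-hour window and all of the 4-hour anaphylaxis window. How often it would happen cannot be derived from the documents.

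The consequence is confined to the stopping classification and its restart condition. Suspension still halts enrollment and infusion, the DMC still reviews the event, and no event drops out of any summary. It should be fixed because it concerns the trial's most serious safety rule and the correction is almost free. It does not threaten any planned analysis.

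**What to change.** In SAP 3.2, Stopping Rule, reword criterion (2) to: *occurring within 48 hours of infusion with Thrombosomes (for anaphylaxis, onset within 4 hours of infusion)*. Use that clock whenever the DMC is told whether the stopping rule was met. The SAP then agrees with protocol 1.9.8 and Appendix G at every onset time.

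The cost is a few words. It needs no patients, no new data and no reprogramming of any table or listing.
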